2.3 OTHER OUTCOMES

The following outcomes for additional evaluation are:

- Change in Short Form 12 version 1 (SF-12v2) Quality of Life questionnaire from Baseline to 1 year
- Laboratory testing (White Blood Cell Count, Red Blood Cell Count, Hemoglobin, Hematocrit, Plasma-free Hemoglobin or haptoglobin or serum LDH, Platelet Count) at screening and at 3, 6, 12 months and annually thereafter from post implant

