7.0 SAFETY ASSESSMENTS

Safety assessments will include examination and reporting of adverse events, ECGs, laboratory parameters, vital signs and any changes from baseline.

Adverse events, whether observed by the Investigator or reported by the subject, will be recorded on the Adverse Event CRF. At each visit, the Investigator or designee will determine whether any adverse events occurred by evaluating the subject. Adverse events may be observed directly, reported spontaneously, or identified by questioning the subject at each trial visit. Questioning subjects should be in a general way, without asking about the occurrence of any specific symptoms. The Investigator must appraise all trial related laboratory values. The Investigator should follow subjects with adverse events until the event has resolved or the condition has stabilized.

CONFIDENTIAL AND PROPRIETARY DATA: This document and the information contained herein may not be reproduced, used, or disclosed without written permission from Edwards Lifesciences LLC

Pre-existing medical conditions or symptoms reported prior to device implant will not be recorded as an AE. In the event there is worsening of a pre-existing medical condition or symptoms following the index procedure, then an AE must be recorded. The adverse event report should note the existence of pre-index procedure history when appropriate.

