7.9 LABORATORY TESTING

Blood data (red blood count, white blood count, hematocrit, hemoglobin, platelet count, and plasma-free hemoglobin or haptoglobin or serum LDH) will be collected POD 180-240 (optional), POD 365-435, and annually thereafter until the trial ends.

For all measured blood parameters, individual results will be compared to documented normal ranges. The Investigator will determine for each parameter that is out-of-range whether the value is abnormal not clinically significant, or abnormal clinically significant. Since summary statistics involving laboratory parameters will be provided, an out-of-range value does not necessarily constitute an AE; other signs and symptoms must be taken into an account in order to report the occurrence of an AE.

Coagulation profile (which may include prothrombin time [PT], or partial thromboplastin time [PTT], or international normalized ratio [INR]) will be collected at the POD 180-240 (optional visit) and annually thereafter, coagulation profile will only be determined for subjects on anticoagulant therapy.

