9.1.4 OTHER OUTCOMES ANALYSIS

The change in Short Form 12 version 1 (SF-12v2) Quality of Life questionnaire from screening to 1 year will be summarized by N, mean, and standard deviation.

Blood data will be analyzed to determine if significant subclinical and unreported hemolysis is occurring due to the implant of the trial valve. A trend analysis of two postoperative data points will be conducted to determine if hemolysis is increasing over time. The following parameters will be included in the trend analysis: plasma-free hemoglobin, haptoglobin, serum LDH, hemoglobin and hematocrit.

For all measured blood parameters, individual results will be compared to documented normal ranges. The Investigator will determine for each parameter that is out-of-range whether the value is abnormal not clinically significant or abnormal clinically significant and summary statistics will be provided.

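### Section 9.1.4 asks whether hemolysis is due to the implant, but neither of its stated methods uses the subject's screening value

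*Combined protocol and SAP*

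**What the plan says.** Section 9.1.4 (Other Outcomes Analysis) states the question: "Blood data will be analyzed to determine if significant subclinical and unreported hemolysis is occurring due to the implant of the trial valve". It then gives two methods.

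- **Trend.** "A trend analysis of two postoperative data points will be conducted to determine if hemolysis is increasing over time". It covers plasma-free hemoglobin, haptoglobin, LDH, hemoglobin and hematocrit. The two visits, the model and any test are not named.
- **Normal ranges.** "For all measured blood parameters, individual results will be compared to documented normal ranges". The Investigator then rates each out-of-range value, and summary statistics follow. Section 7.9 has the same rule: "The Investigator will determine for each parameter that is out-of-range whether the value is abnormal not clinically significant, or abnormal clinically significant".

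The screening values exist. Section 2.3 schedules the blood tests "at screening and at 3, 6, 12 months and annually thereafter from post implant", and the Synopsis also lists screening. Section 7.0 says: "Safety assessments will include examination and reporting of adverse events, ECGs, laboratory parameters, vital signs and any changes from baseline". No visible analysis section says how that is to be done for blood data. Other outcomes do use the starting value: 9.1.4 itself takes SF-12 as a change from screening, and Sections 8.2 and 9.1.3 compare NYHA class with the preoperative class.

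**The concern.** The question is one of attribution. The trial has a single arm (Section 4.1) and 9.1.4 names no outside reference for these markers, so the subject's own screening value is the only comparator within the trial. Eligibility does not ensure normal starting values. Exclusion 21 removes acute anemia with hemoglobin below 10.0 g/dL, and no criterion limits LDH, haptoglobin or plasma-free hemoglobin.

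The two methods fall short in different ways. Under the normal-range comparison, a subject who is out of range before and after surgery is flagged although nothing changed, while one who worsens but stays in range is not flagged. The trend, taken between two points after surgery, cannot show what happened at surgery.

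Section 7.9 says an out-of-range value is not necessarily an adverse event. The 9.1.4 analysis is therefore the described check for hemolysis that was never reported as an event. Without the screening value it could give a false signal or false reassurance.

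**Working it through.** **1. Plan figure.** There is none to reproduce. The documents state no sample size, SD, alpha or expected out-of-range rate for this analysis. Enrollment was 934 (Synopsis). All other inputs below are assumptions chosen to show how the methods behave.

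**2. Normal-range comparison.** Let q be the share out of range at screening, assumed to persist, and e the share of new abnormality among those normal at screening.

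Flagged share = q + (1 − q) × e. Pre-existing part of the flags = q / flagged share.

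With e = 5%:

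| q | Flagged share | Pre-existing part |
|---|---|---|
| 5% | 0.05 + 0.95 × 0.05 = 9.8% | 51% |
| 20% | 0.20 + 0.80 × 0.05 = 24.0% | 83% |
| 40% | 0.40 + 0.60 × 0.05 = 43.0% | 93% |

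The new abnormality is 5% in every row, yet the flagged share runs from 9.8% to 43.0%. With e = 0 the flagged share is simply q. For an assumed 800 subjects with values, q of 5%, 15% or 30% gives 800 × 0.05 = 40, 800 × 0.15 = 120 or 800 × 0.30 = 240 flagged subjects with no new abnormality at all. Tabulating new abnormality only among those normal at screening returns e directly.

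**3. Two-point trend.** Let b be a subject's stable level, s a constant step at implant, and u0, u1, u2 random error at screening and at two postoperative visits. Then y0 = b + u0, y1 = b + s + u1 and y2 = b + s + u2.

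- y2 − y1 = u2 − u1, with mean 0 whatever s is. The step is invisible.
- y2 − y0 = s + u2 − u0, with mean s. The step is visible.
- b cancels from both differences, so a stable pre-existing abnormality does not contaminate the trend.

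A simulation with 934 subjects (SD 1 for b, SD 0.5 for each error) agrees. With s = 1, the mean of y2 − y1 was −0.03 and the mean of y2 − y0 was 1.02. The correlation of y2 − y1 with b was 0.02.

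**4. Precision of a paired change.** Assume a paired SD of 60 U/L for LDH and 400 subjects with LDH at both times. SE = 60/√400 = 3 U/L, and 1.96 × 3 = 5.9 U/L. This shows that a mean shift could be estimated closely. It does not show that a shift of that size matters clinically, and 9.1.4 asks about significant hemolysis.

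**5. Why the new-abnormal rate is not enough alone.** A subject abnormal before surgery for one reason and abnormal afterwards because of the prosthesis falls in the abnormal-to-abnormal cell. A headline rate restricted to subjects normal at screening would leave that subject out, so the change among those already abnormal must be reported too.

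**The case against.** The other side has six arguments.

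- **Section 7.0 already covers change from baseline.** It does, so a reader who infers that the plan ignores baseline altogether goes too far. But 7.0 gives no method and 9.1.4 does not carry it out.
- **The detail may be elsewhere.** Section 9.0 points to other analysis documents whose references are blanked out, and a screening comparison may be specified there. This cannot be checked. Section 9.1.4 is legible, however, and should agree with 7.0.
- **The trend suits its stated purpose.** This stands. A reader might infer that pre-existing abnormality also distorts the trend. The algebra above shows that a stable abnormality cancels in a within-subject difference; the mixing arises only in the normal-range comparison.
- **Range comparison is not the only filter.** The Investigator judges clinical significance. Section 7.0 excludes pre-existing conditions from adverse events but requires worsening to be recorded. The visit tables in Section 6.2 require a repeat draw when plasma-free hemoglobin exceeds 40 mg/dl. These steps make a naive reading of a high out-of-range rate less likely. A significance rating still does not say whether the abnormality is new.
- **Change from screening does not prove cause either.** This is right and limits the remedy. In a single arm, the change combines removal of the native valve, the operation and the prosthesis.
- **The consequence is limited.** This also stands. Hemolysis is separately a primary safety endpoint, reported under 9.1.2.1 as early percentages, late linearized rates and Kaplan-Meier estimates. Nothing here suggests that result is wrong.

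**Conclusion.** The point holds, within limits. Neither method named in 9.1.4 uses the screening value, so as written the section cannot separate new from pre-existing abnormality, and it cannot see a sustained step at implant. Summary statistics by visit would not close the gap, because they give neither within-subject change nor new abnormality.

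The effect is confined to the subclinical hemolysis assessment, an other outcome; no primary result or decision rule changes. Its size cannot be stated from the documents. The out-of-range shares, their full persistence, the 800 and 400 subjects and the 60 U/L are all assumptions. What does not depend on them is the direction: the flagged share grows with q, and a constant step gives an expected postoperative difference of zero.

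**What to change.** Add to 9.1.4, for each marker and only where the same marker was measured at both times:

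1. the within-subject change from screening at each scheduled postoperative visit, with a 95% CI;
2. the full shift table (screening normal or abnormal, by postoperative normal or abnormal), reporting both the new-abnormal rate among subjects normal at screening and the change among those already abnormal.

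A breakdown by core-lab PVL grade at the visit is optional. Keep the postoperative trend for increase over time, and name the two visits it uses. Describe the change from screening as the net change after surgery (native-valve removal, operation and prosthesis together), not as proof of an implant effect. Label the POD 195 results as coming from a selected group, since Section 6.2.1 requires that visit only for PVL above mild or an implant-related conduction disturbance.

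The cost is a few tables on data already scheduled, with no new visits or draws. The downside is that plasma-free hemoglobin, haptoglobin and LDH are alternatives in the schedule, so subjects whose marker changed since screening drop out of the paired tables. Report the number of pairs for each marker and visit.

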9.1.5 MISSING DATA

All statistical tests on the effectiveness endpoints will be performed using only those subjects with available data required for endpoint analysis. No missing value imputation will be performed.

9.2 ADDITIONAL INFORMATION

The following additional information will be provided:

- the follow-up duration information, including the mean follow-up, standard deviation and range of follow-up and cumulative follow-up in late-patient years will be determined and reported;
- subject compliance data for follow-up visits, NYHA functional classification data, echocardiographic data and clinical laboratory results will be determined and reported;
- listing of AEs/complications by subject ID number;
- case summaries of each death with a determination whether the death represents an early or late death;
- available autopsy reports;
- case summaries of explants and reoperations;
- analyses of valves when a valve was explanted or an autopsy performed;

- summary of subjects not completing the trial due to lost to follow-up, explant or death; and
- confounding factors such as gender, age at implant, preoperative NYHA Class, concomitant procedures, co-existing (cardiac) conditions, valve size, etc., will be considered in a hazard regression analysis to determine which factors may affect the incidence of reoperation, explant and death;
- summary of subject complaints received.

10.0 TRIAL COMMITTEES AND CORE LABORATORY

10.1 CLINICAL EVENTS COMMITTEE

A CEC consisting of independent physicians familiar with the treatment of valvular heart disease and cardiac surgery will evaluate the adverse events including adverse events resulting in death as outlined in their charter and adjudicate these events for their relatedness to the trial device, and the trial device procedure.

Members of the CEC will not have scientific, financial, or other conflict of interest related to the Sponsor or the Investigators. CEC members must sign a non-conflict-of-interest statement in this regard.

10.2 DATA MONITORING COMMITTEE

A DMC composed of two or more independent physicians including a cardiothoracic surgeon and cardiologist, and a statistician evaluated the rates of OPC's, study endpoints and serious adverse events including deaths and explants for all subjects in the clinical investigation as well as the hemodynamic performance of the EDWARDS INTUITY aortic valve during the enrollment phase. Members of the DMC did not have scientific, financial, or other conflict of interest related to the Sponsor or the Investigators. DMC members signed a non-conflict-of-interest statement in this regard.

The DMC activities and meeting schedule was regulated by the DMC Charter.

10.3 ECHOCARDIOGRAPHY CORE LAB

The purpose of the Echocardiographic Core Laboratory is to ensure unbiased, timely and consistent analysis of these diagnostic data. The Core Lab is responsible for evaluating changes in subject status over the course of the trial based on serial echocardiographic studies conducted in the same subject. Personnel at the Core Lab will have training and experience appropriate for analyzing Doppler Echocardiography data. The Sponsor will ensure that Core Lab personnel are familiar with the valve. The Sponsor or its designee will periodically perform audits of the Core Lab. The Sponsor will review the data provided by the Core Lab as appropriate.

Doppler echocardiograms must be conducted as described in xxx; original videotapes or CDs of Doppler echocardiograms will be sent directly from the trial sites to the Core Lab. The Core Lab will review the Doppler echocardiograms upon receipt and notify the site promptly if the quality of the echocardiogram is insufficient for analysis.

11.0 DATA INTEGRITY, COLLECTION AND QUALITY ASSURANCE

To protect subject confidentiality, the subject's name must not appear anywhere on the imaging media sent for evaluation by the Core Lab, or on copies of supporting documentation removed from the investigational center. Each page should be identified with the subject's ID number only. All other subject identifiers (e.g., subject name, address, medical record number etc.) are to be obscured. Electronic records will be compliant with 21 CFR Part 11.

11.1 DATA COLLECTION

All required data for this investigation are to be collected on standardized eCRFs for individual enrolled subjects; sample eCRFs are provided in xxxxx. The eCRF must be electronically signed by the Principal Investigator or co-Investigator listed in the Clinical Studies Agreement and/or Delegation of Authority Log. If for any reason the eCRFs are unavailable and/or inaccessible, paper CRFs will be provided by the Sponsor to be completed, signed by the Principal Investigator or designee and submitted to the Sponsor. Case Report Form Instructions will be provided to assist the Investigator(s) and appropriate investigational staff in the completion of the required eCRFs.

CONFIDENTIAL AND PROPRIETARY DATA: This document and the information contained herein may not be reproduced, used, or disclosed without written permission from Edwards Lifesciences LLC

Source documents are original documents, data, and records from which the subject's CRF data are obtained. These include, but are not limited to, hospital records, clinical and office charts, laboratory records, and correspondence.

Electronic CRFs must be kept current to reflect enrolled subject status during the course of the investigation.

11.2 DATA QUALITY ASSURANCE

Edwards Lifesciences clinical affairs and data management departments have quality assurance procedures to ensure that complete, accurate and timely data are collected, that the Investigational Plan requirements are followed and that all complications and adverse events are reported in a timely manner.

Electronic CRFs are used for collecting and recording of data for enrolled subjects at all trial sites. Investigators or their designees are responsible for the timely completion of these forms.

Entered data are reviewed to identify inconsistent or missing data and adverse events. Data problems will be addressed by phone or written communication with the trial sites and/or during site visits. All forms and data files will be secured to ensure confidentiality.

Investigators are to maintain all source documents required by regulation, including diagnostic test reports, laboratory results, completed CRFs, supporting medical records and informed consents. The source documents will be referenced during regular monitoring visits to verify the information documented on the CRFs.

Follow-up Doppler echocardiograms will be evaluated by the designated Echo Core Lab. A standardized written report generated by the Core Lab for each Doppler echocardiogram will be entered into an electronic database maintained by the Sponsor. The Clinical Site Manager or Sponsor designee shall notify the Investigator should there be any indication of a complication or discrepancy that the Investigator may not have noted. This will allow the Investigator an opportunity to further review the test results and clarify the findings if necessary.

CONFIDENTIAL AND PROPRIETARY DATA: This document and the information contained herein may not be reproduced, used, or disclosed without written permission from Edwards Lifesciences LLC

The electronic database is subject to predefined electronic data checks to identify potential discrepancies and inconsistencies. Furthermore, trial content data reviews are conducted to ensure that data collected are scientifically and medically valid. Regular feedback and reports will be provided to the site manager, so that all queries can be resolved in a timely fashion.

12.0 INVESTIGATOR RESPONSIBILITIES

The Investigator is responsible for ensuring that this clinical trial is conducted according to the Investigator Agreement, Protocol, all conditions of FDA and IRB approval and applicable FDA regulations. Written IRB approval of the protocol and ICF must be provided to the Sponsor.

Subjects were informed that their medical records will be subject to review by the Sponsor, its authorized designee or representatives of FDA. Subjects were informed that they may withdraw at any time without prejudice to future care. The informed consent provided by each trial site's IRB was signed prior to trial participation. The original signed informed consent for each subject must be retained by the Investigator and is subject to review by the Sponsor and the FDA. A copy of the informed consent will be provided to the subject.

Other specific responsibilities of the Investigator include:

Financial Disclosure:

The Investigator provided sufficient and accurate financial disclosure information prior to trial, and will promptly update the Sponsor of relevant changes during the course of the trial and for 1 year following completion of the trial.

.

Inspection:

The Investigator shall permit authorized FDA employees at reasonable times and in a reasonable manner to enter and inspect any establishment where devices are held, inspect and copy all records relating the investigation, to inspect and copy records that identify subjects when the FDA has reason to suspect that records are incomplete, inaccurate, false or misleading.

12.1 INVESTIGATOR RECORDS

Investigators will maintain complete, accurate and current trial records for whichever of the following periods is shortest:

- a. A period of two years after the date on which the FDA approves the marketing of the device for the purpose that was the subject of the trial.
- b. A period of five years after the date on which the results of the trial are submitted to the FDA in support of the marketing of the device for the purpose that was the subject of the trial.

If the Investigator withdraws from the responsibility to maintain records, the custody of records may be transferred. Notice of transfer shall be given to the FDA no later than 10 working days after transfer occurs.

Investigator records shall include the following materials:

Correspondence:

Documentation of all verbal and written correspondence with FDA, the Sponsor or its designee including the Clinical Monitor, the Medical Monitor, the DMC and other Investigators regarding this clinical trial or any subject enrolled therein.

Device Accountability:

Accountability records of receipt, use and disposition of all investigational devices and other trial materials, including:

- The type and quantity of the devices, dates of receipt and serial or lot numbers
- The names of all persons who received, used or disposed of each device and
- Why and how many units of the device are returned to Edwards Lifesciences, or otherwise disposed of.

Subject records:

Available subject records will include: signed informed consent, supporting documents (admission summary, operative reports, discharge letters, pertinent consultation reports diagnostic tests, laboratory tests, medical records, etc.) and records of exposure of each subject to the device.

Investigational Plan (Trial Protocol):

A Trial Site Regulatory binder will be maintained by the Investigator and site coordinator and will include a current copy of the Investigational plan including the IFU of the trial valve and other specified documents as listed in the binder table of contents.

Unanticipated Adverse Device Effects:

The Investigator will maintain records of all reports and information pertaining to unanticipated device effects.

IRB Information:

All information pertaining to IRB review and approval of this clinical trial including a copy of the IRB letter and that the IRB approved the Investigational Plan, a blank ICF approved by the IRB, and certification from the IRB Chairman that the IRB complies with FDA regulations (21CFR, Part 56).

Investigator Agreements:

The Investigator will maintain copies of signed Investigator Agreements and current CVs of all participating clinical trial staff members.

Other:

The Investigator will maintain any other records that may be required by applicable state or U.S. federal laws.

Investigator Reports:

The Investigator will prepare and submit the following reports:

Withdrawal of IRB Approval:

If applicable, withdrawal of approval shall be reported to the Sponsor within five working days. The Investigator will provide a written report of the reason(s) approval was withdrawn.

Progress Reports:

The Investigator will submit progress reports to the Sponsor in the form of completed CRFs. The same forms will be used at all trial sites for the recording of data on the findings of follow-up evaluations and complications. In addition, the Investigator may be asked to submit progress reports to the Sponsor and the reviewing IRB that include the number of trial subjects, a summary of follow-up data and AEs/complications and a general description of trial progress.

Final Report:

The Investigator shall submit a final report within three months of termination, completion of the trial or completion of the Investigator's participation in the trial, to the Sponsor and the IRB.

Deviations from the Trial Protocol:

The Investigator will not deviate from the protocol without the prior written approval of the Sponsor except in medical emergencies or in unforeseen, isolated instances where minor changes are made that will not increase the subject's risk or affect the validity of the trial. Any subsequent revisions to the protocol, including the Informed Consent Form and the Case Report Forms, other than very minor revisions, must be approved by the Sponsor, the FDA, and the IRB. In medical emergencies, prior approval for protocol deviations will not be required, but the Sponsor or its designee and IRB must be notified within 5 working days of the incident. Periodic monitoring of protocol compliance will be performed for each site. Deviations will be documented on the appropriate case report form.

Other Reports:

Upon the request of FDA, the reviewing IRB, or the Sponsor, the Investigator will provide accurate and timely information about any aspect of the clinical trial.

